3.4 Data analysis	
3.4 Ethical considerations	
4. Implementations	11
4.1 Project group	11
4.2 Project management and organization	11
References	12

1. The epidemic of obesity

Obesity, defined as "abnormal or excessive fat accumulation that presents a risk to health" (1) and a body mass index (BMI) of \geq 30, represents a major health challenge and economic burden for welfare systems worldwide (2,3,4). For the individuals affected, having obesity is associated with a broad range of adverse health consequences ranging from non-communicable diseases, such as diabetes type 2, metabolic syndrome (5), liver disease (6) and cardiovascular disease (7) to negative impacts on mental health (8), higher risk of urinary incontinence (9, 10) and can consequently lead to impaired quality of life (11). Today, approximately one out of five adults are categorized with obesity in Norway, and the trend in obesity rates is predicted to further increase, with the highest prevalence reported among women (3, 12, 13). More women than men are also at risk of developing severe forms (\geq 35 BMI) of obesity (3,12).

A report from Menon Economics revealed that the three major economic impacts of obesity were: disease burden (costs related to the burden of obesity such as pain and shortened life span), productivity costs (loss of productivity in the labor market due to absence from work and other obesity-related health reasons), and medical costs (costs related to diagnosis and treatment of obesity-related conditions) (2). The total economic cost of obesity in Norway was estimated to be approximately 68 billion NOK yearly (2). Disease burden represented the highest cost (39 billion NOK), followed by productivity costs (17 billion) and medical costs (12 billion NOK) (2).

Living with obesity is reported to account for 80-85% of the risk of developing noncommunicable diseases such as diabetes type 2 (14). Hence, women with obesity experiences a 28 times greater risk of developing diabetes type 2 than women of normal weight (15). Among women with BMI of \geq 35, this increases to a 92 times greater risk (15). Guidance on regular physical activity, exercise and healthy eating is traditionally the first measure taken for patient who undergo treatment for obesity (3). Physical activity is defined as "any bodily movement produced by skeletal muscles that requires energy expenditure above resting level" (16). Exercise is defined as "a regular and structured subset of physical activity performed deliberately with a specific purpose, for instance improving some aspects of health or physical fitness" (16). Increased physical fitness and improved health can reduce the risk of the adverse consequences of obesity, independently of weight loss (17,18, 19). Hence, physical activity and exercise can minimize the risk of premature mortality and further development of non-communicable diseases related to obesity (such as diabetes type 2) (20, 21, 22,). However, the health benefits of physical activity and exercise rapidly decrease if it is not performed regularly (23) Fewer women with obesity are reported to meet the Norwegian government's recommendation for physical activity (150 to 300 minutes of moderateintensity or 75 to 150 minutes of vigorous-intensity per week), compared with normal weighted women (16 % versus 57%) (24, 25). Having multimorbidity because of obesity, is also associated with not following guidelines (26). Further research investigating methods on getting more women with obesity regularly active are therefore needed.

1.1 "Exercise as medicine"

Treatment for obesity in the primary healthcare service in Norway is largely coordinated by general practitioners (GP) (2). Today, GPs can prescribe "exercise as medicine" to patients with diabetes type 2, hypertension, obesity or cardiovascular disease (27). "Green prescriptions" (tailored advice and guidance on lifestyle factors related to development of disease, such as physical activity, exercise and healthy eating) was first founded in 2003 as an alternative to medical treatment for patients with diabetes type 2 and hypertension (28). Green prescriptions involve a specific target payment code for medical procedures "101", meaning that GPs receive financial incentives to discuss physical activity and healthy eating with the patient (28).

However, 41% of GPs in 2006 reported that they had newer prescribed green prescriptions to their patients (29, 30). Attalin et al. (2012) reported that 63% of GPs listed patient's nonadherence to the tailored advice they were given as main barrier for not implementing green prescriptions in their practice (31). Low adherence may be associated with that the current green prescription model is lacking sufficient follow-up of patients (29). To increase patient's adherence, GPs are requesting a follow-up alternative that includes social support, nutritional guidance, and reduced costs for exercise participation (29). Low adherence can also be associated with that GPs are found to have less positive attitudes towards health promotion in primary health care (32). Attalin et al. (2012) reported that only 52% of GPs wished to acquire skills in consulting patients on physical activity and exercise (31). Thus, increase GPs knowledge on mental and physical health outcomes by utilizing exercise as medicine, may also rise the use of green prescriptions. According to the "ABC framework for prescribing exercise as medicine" developed by O'Regan et al. (2021) (33), it is highlighted that providing patients with in-person coaching is essential to maintain adherence. Lundqvist et al. (2019) (34) observed that patients who received structured coaching by health personnel for six months became more active, and coaching was also correlated with positive predictors for exercise and physical activity adherence (self-efficacy and stages of change) (34). This was also observed in patients with obesity, where offering in-person coaching and social support was the greatest promotors for exercise adherence (35). The "ABC framework" also states the importance of establishing collaborations with professions such as exercise professionals to be able to provide sufficient individualized follow-up and coaching of patients (21, 35). This was confirmed by Tulloch et al. (2005) (36), where the most effective intervention to improve exercise adherence among patients was a collaboration between GPs and exercise professionals. Therefore, in-person coaching by an exercise professional may have the means to get more patients with obesity regularly active, and can potentially be the follow-up alternative the current green prescription model is lacking (35,37).

Considering the expenses and practical considerations associated with in-person coaching, has former studies displayed the advantage of web-based behavioral support for patients with lifestyle diseases such as obesity (38). It is a timesaving, cost effective, and can potentially be an important contributor for a sustainable green prescription model. However, web-based behavioral support often proves to have poor completion rate, and need to be combined with

face-to-face guidance and feedback in order to increase adherence (39, 40). For instance, Ellev et al. (2019) (41) observed that a follow-up model, consistent of a combination of inperson exercise coaching and telephone calls improved adherence to exercise and physical activity. However, when combining in-person coaching and web-based behavioral support, there is still limited knowledge on how frequent in-person coaching needs to occur, in order to increase adherence. For instance, Ries et al. (2003) (42) observed that providing patients with monthly in-person coaching, and weekly telephone calls on the non-supervised weeks. only produced modest improvements in adherence. More knowledge on frequency of followup is therefore essential for an approach towards an economical sustainable green prescription model. For example, mean costs per patients for different frequency of in-person coaching are: four sessions monthly: 2400 NOK/monthly per patient. two sessions monthly 1500 NOK/monthly per patient NOK or one session monthly. 1050 NOK/monthly per patient. In discrepancy, the potential expense of sessions with an exercise professional may be profitable in the long run, and the general mean cost per patient for in-person follow-up is lower compared with the current costs associated with obesity and non-communicable diseases (2).

2. Purpose

The ultimate ambition of this project is to identify an economical sustainable model to get women with obesity regularly active, with improved health and physical fitness, and thus lower risk of developing severe health challenges.

The current study will be the first step in the development of such a model, where we aim to conduct a pilot/feasibility study to prepare for a large-scale study by establishing estimates of effect sizes, and to investigate barriers for successful implementation.

The ABEL Feasibility Study will evaluate the effect of three follow-up models with different frequency of physical follow-up by an exercise professional, on exercise adherence and total physical activity level. A secondary objective of this project is to evaluate if these follow-up models can improve mental and physical health and physical fitness in women with obesity. Finally, we aim to identify potential barriers to successful implementation of a "green prescription" among participants, GPs and exercise professionals.

2.1 Research aims

- In women with obesity (BMI≥30), what is the effect of in-person exercise coaching (high vs. medium vs. low dosage) on exercise adherence and total physical activity level?
- 2. In women with obesity (BMI≥30), what is the effect of in-person exercise coaching (high vs. medium vs. low dosage) on mental health variables (quality of life, self-efficacy and barriers and motivation to exercise)?

- 3. In women with obesity (BMI≥30), what is the effect of in-person exercise coaching (high vs. medium vs. low dosage) on health (glycated hemoglobin, cholesterol, blood pressure, waist circumference, BMI and urinary incontinence) and physical fitness (aerobic endurance, muscular strength)?
- 4. Is adherence to exercise and succeeding health effects associated with the exercise professionals' level of education and knowledge base?
- 5. What are the participant's experiences, barriers and facilitators of participating in the ABEL-project?
- 6. What are the general practitioners' experiences, barriers and facilitators of using the "green prescription"?

3. Method

3.1 Women with obesity (n = 200)

In the present feasibility study, women with obesity (BMI of \geq 30, n=200) will be recruited to a 20-week randomized control trial (RCT) with four arms (Table 1). The groups are provided the same frequency (each week) of follow-up by the exercise professional, with a different dose of in-person exercise coaching and web-based behavioral support. Enrollment will be limited to age between 18 to 65 years, no fitness club membership six months prior to recruitment, low-active (<150 minutes of moderate-intensity or 75 minutes of vigorousintensity per week), Norwegian speaking, and in possession of a smartphone. Exclusion criteria's are: chronic disease or pathology (e.g severe hypertension 180/110 mm Hg), heart disease or lung disease hindering exercise, changing GP during the intervention, functional impairment due to injuries hindering physical activity and exercise, and traveling during the intervention period, or at the time baseline and follow-up measures will be conducted.

Participants will be recruited via social media platforms (Facebook and Instagram) from rural (Sandnessjøen, Narvik, Svolvær, Sørumsand, Sogndal and Førde) and urban locations (Oslo, Bergen, Stavanger, Tromsø, Bodø and Arendal) spread across Norway. An advertisement on Facebook and Instagram will be posted, including contact information to one of the project fellows. Interested participants can contact the research fellow, and is informed to contact their GP. Due to practical reasons associated with the geographical spread of the project, members from the project group at NSS are not able to perform health screening of all participants. Therefore, to ensure that none of the participants have any contraindications for participating in the project, all participants will undergo a general health screening at their GP.

Intervention arms				
One in-person exercise session with the exercise				
professional/weekly.				
A total of 20 hours of in-person coaching during the 20 weeks				
of intervention.				
Two in-person exercise session with the exercise				
professional/monthly, and 15 minutes web-based behavioral				
support on the non-supervised weeks.				
Total of 10 hours in-person coaching during the 20 weeks				
intervention.				
One in-person exercise session with the exercise				
professional/monthly, and 15 minutes web-based behavioral				
support on the non-supervised weeks.				
Total of five hours of in-person coaching during the 20 weeks				
intervention.				
Will be asked to continuing with normal life, and will receive				
regular follow-up care from their GP. This group will be				
giving the "Norwegian Directorate of Health's"				
recommendations for physical activity and nutrition (43) and				
will have access to the ABEL-app in order to register physical				
activity and exercise, but will not be provided any coaching				
during the 20 weeks.				

Table 1. Intervention arms (High, medium and low dosage in-person exercise coaching and control).

For group HIGH, MEDIUM and LOW dosage of in-person exercise coaching, the exercise professionals will prescribe exercise programs tailored to the individual needs, as well as give advice about healthy eating and a balanced meal plan, including ideas, recipes and shopping lists. All participants will also get access to a web-based behavioral support (ABEL technologies), where individual exercise programs will be available, as well as nutritional guidance, graphs for progression and motivational notifications for achievement of goal settings. Via the ABEL-app, participants will enter physical activity and exercise data (type of activity, duration, intensity, frequency etc.), including the sessions without the exercise professional. The parameters that are logged in via the ABEL-app include rate of perceived exertion (RPE) for all activity, duration, intensity and type of activity. Weight lifted will also be logged for resistance exercise.

3.1.1 Exercise professionals (n=25)

A total of 25 exercise professionals, working full time as a personal trainer will follow up the participants at one of the following fitness clubs: Feel24, PT-group, Nr1 Fitness, Trento or Spenst. These fitness clubs are located in the same area the participant lives and receives regular follow-up care from their GP. To minimize error caused by limited knowledge of the ABEL-app, and to ensure that the exercise professionals know how to use this system for

coaching participants and data collection, the exercise professionals have finished a webbased onboarding program, consisting of six modules, of 45 to 60 minutes. In the five first modules, the exercise professionals were educated in the functionality of the ABEL-app. The sixth module was led by two members from the ABEL-project group, where the exercise professionals learned how to conduct testing of participants and instructed in standardized test protocols. In addition, instruction videos for all test protocols will be uploaded on the ABEL-app.

To be included in the research project as an exercise professional, the qualifications and requirements are:

- A minimum of three years' experience working part-time as a personal trainer, and delivered ≥ 80 training sessions/per month, in three of the last five months, with one of the following qualifications:
 - 1) Higher education: bachelor/master in sports science, or other relevant health education (physiotherapy, nursing, osteopath, chiropractor).
 - 2) Practical experience: A personal training education (one-year education/60 credits), well as 2000 hours of delivered exercise sessions with clients.
- Completed an exam, developed by researchers at NSSS and Kristiania University College, that covers knowledge in: central elements of exercise (anatomy, physiology, biomechanics, aerobic endurance, and muscular strength), physical activity and health, coaching and motivation, source criticism and methodology, and exercise among patients with obesity. The test scores will be used to evaluate associations between the exercise professionals' level of competence and participants adherence to exercise and/or improvement in health and physical fitness. The project will therefore also obtain informed consent from the exercise professionals.
- Signed "professional ethics guideline" document.
- Completion of "Norway's Anti-Doping Agency's" and "Norway's counseling About Eating Disorders eLearning module.

3.1.2 Random allocation

Each participant will be randomly assigned (1:1:1:1) to one intervention group, HIGH, MEDIUM, LOW or CONTROL following a simple computer-based randomization program. All participants included in the study will conduct the baseline assessments before the randomization procedure. The study design will not allow for further masking of study participants or the exercise professional (caregivers to the interventions). Those from the research group involved in inclusion of the participants or follow-up measurements will not have access to the group allocation list. Further, all measurements will be completed and plotted without the research group information of group allocation. The statistical analyses will be done in SPSS, following a predefined analysis plan and before unmasking the study arms.

3.2. General practitioners (n=8)

In addition to the RCT, the project will recruit GPs (n=8) from clinics at the rural and urban locations to participate in an in-depth interview with researchers from NSSS (see 3.3). GPs will be recruited to provide more in-depth understanding on reasons for what the current green prescription model is lacking.

3.3 Outcome measures

Date will be collected at baseline, continually during, and immediately following the intervention period.

Monitoring adherence to subscribed exercise sessions:

Measures of adherence will be collected through the ABEL-app. Sessions performed with the exercise professional will be logged through the ABEL-app of the exercise professional, while sessions performed independently will be logged through the ABEL-app of the participant. Adherence will be measured by attendance (percentage of exercise sessions completed out of exercise sessions offered), as well as intensity (physical exertion of sessions) and duration (duration of sessions) (44).

Questionnaire (approximately 25 minutes to complete):

- **Background information:** Covering age, smoking, level of education, household income. In addition to information about physical activity behavior (fulfillment of physical activity recommendations, as well as weekly frequency, duration and modes of physical activity).
- **Health-related quality of life**: Will be measured by a Norwegian version of The MOS 36-item short-form health survey (SF-36) (45).
- **Self-efficacy**: Will be measured by a Norwegian abbreviated validated version of the Self-Efficacy Survey developed by Sallis et al. (46).
- **Perceived social support from family and friends**: Will be measured by a Norwegian version of a previous validated survey (47).
- **Stages of change:** Will be measured with a previously conducted questionnaire on exercise professionals' effect on changing attitudes towards physical activity according to upward moving in the stages of change model (48). To achieve high cross-language validation when translating the English version into Norwegian language, we used a forward-backward translation technique, involving three members of the research group. A bilingual acquaintance of the research group with English as mother tongue will finally assured the quality by comparing the "new" English version" with the original version.
- **Barriers to exercise:** Questions will be based on identified barriers in a previous study among Norwegian adult population (n= 12 504) (49) and among fitness club members (50). Eighteen barriers will be included in the questionary.
- **Motivation for exercise and physical activity:** Will be measured by a Norwegian version of the validated survey BREQ-2 (51).

 Urinary incontinence: Will be measured using a Norwegian version of the Incontinence Questionnaire-Short Form (ICIQ-UI SF) (52). Awareness and knowledge about pelvis floor muscles exercises will be assessed by single questions: "Do you do pelvic floor muscle exercises?" If yes, how many times weekly?" "If yes, has your exercise professional provided you any coaching on pelvic floor muscle exercises?"

At follow-up, we will add questions regarding how satisfied participants are with the digital and physical follow-ups, as well as perceived social support from their exercise professional during the trial period.

Health factors:

- **Blood pressure, waist circumference and BMI:** Measures of blood pressure, waist circumference and BMI (height and weight) will be conducted during health screening at the GP. These variables are strongly associated with development of non-communicable diseases and can therefore be a low-cost indicator of general health which is minimally intrusive for the participant (53). Data will be scanned and sent to NSSS via password protected zip-files after the posttest, and stored on a secure data area.
- **Glycated hemoglobin and cholesterol:** Testing self test kits (Tigeni, Norway) will be given to all participant at baseline and follow-up for collection of blood sample markers: glycated hemoglobin and cholesterol (LDL, triglycerides and HDL). All values will be collected through capillary blood drawn from finger pricks. The participants will conduct the finger pricks test at their respected fitness club. The samples will be collected via DHL and sent to Tigeni for further analyses. Data will be collected by the GP and sent to NSSS via password protected zip-files after the posttest and stored on a secure data area. These testing kits have been shown to be reliable and valid for testing for markers as described above (54), and are considered to be practicable for the participants (55). Furthermore, due to the spread among the participants geographically, there is a need for achievable methods for collecting these markers.

Physical fitness:

The exercise professionals will be conducting physical tests of the participants at baseline and at the end of the 20-week follow-up, to evaluate the individual progress in strength and aerobic endurance. The tests will be performed in the same order (aerobic then strength) at baseline and follow-up, with a standardized rest interval of 10 minutes between aerobic and strength measures. The results from strength testing will be sent to NSSS via password protected zip-files and stored on a secure data area. The results from aerobic testing will be logged analog, and sent to NSSS via mail, and plotted manually on secure data area.

• Aerobic endurance: Will be assessed with a standardized incline treadmill-walking test. Changes in working heart rate, reported RPE, and changes in heart rate recovery

after the test will be used to assess relative changes in aerobic capacity (56). Each participant will use the same treadmill at baseline and follow-up in order to avoid any speed and incline variations between different treadmills. Optical heart rate sensors (Polar Verity Sense) placed on the upper arm will be used for optimal heart rate recordings. Speed will be set at a constant of 6 km/h throughout the test, while inclination starts at 0%, and increases by 2% every three minutes. Heart rate and RPE values within the last 30 seconds of each load will be noted and used for estimation of intensity at each inclination. The exercise test will be stopped when the participants reach a reported RPE value of 16 or more, and the participants are asked to stand still and up right for two minutes. Heart rate values at one and two minutes will be recorded and used as measurements for heart rate recovery.

Muscular strength: Will be assessed by a 1-RM estimation test in: chest press, close • grip lat pull down and leg press. All exercises will be performed on the weight machines available at the specific location, and may therefore be slightly different. However, each participant will be tested on the same machine at baseline and followup. Two to three days before the 1-RM estimation test (test day), participants will undergo a familiarization session using each of the exercise equipment, according to the recommendations by Balady et al. (2000) (57). A load the participant perceives as low intensity will be selected for practice of correct lifting and breathing techniques (57). Practice continues until the participant demonstrates proper technique using submaximal loads, in all exercises for 10 repetitions. Participants will be asked to complete 10 repetitions for warm-up, using the load performed at the familiarization session. Thereafter, the load will progressively be increase until the participant reaches nine or less repetitions. Resting periods between attempts will be two minutes with a maximum of six attempts, and three minutes between each specific exercise. Brzycki 1-RM prediction equation (58) will be used to estimate the 1-RM based on the resistance and repetitions performed. The equation is mathematically expressed as 1RM = W/[102.78 - 2.78(R)]/100, where W is the weight used and R is the maximal number of repetitions performed.

In-depth interview:

• Women with obesity (n=15): In parallel with the RCT, 15 participants from the intervention groups (HIGH n = 5, MEDIUM n = 5, LOW dosage n = 5) will be recruited to participate in a semi-structured in-depth interview (approximately 60 min). The interview will be led by researchers from the project group, audiotaped and transcribed verbatim. An interview guide with open-ended questions will be developed by the project group, and based on: 1) Basic Psychological Needs in Exercise Scale (BPNES) (59, 60), that assess the extent to which the psychological needs of the participants were fulfilled during the intervention. BPNES includes three subscales, with four statements per subscale, to assess autonomy, competence, and relatedness. 2) A former investigation in Norway, including 14 questions designed to address factors associated with exercise adherence and drop-out (61). With regards to

the purpose of this project, we will also add questions regarding how satisficed participants where with in-person and digital follow-up by their exercise professional.

• General practitioners (n=8): The GPs recruited in the project will participate in a semi-structured in-depth interview (approximately 45 min). The interview will be led by researchers from the project group, audiotaped and transcribed verbatim. Questions will be based on a previous qualitative study from 2006, conducted on GPs in Norway (29).

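### Week-20 strength and treadmill tests are run by unmasked exercise professionals who also coach, and nothing keeps a coach from testing her own participant

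*Protocol*

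**What the plan says.** **Who tests.** Protocol section 3.3, under physical fitness: "The exercise professionals will be conducting physical tests of the participants at baseline and at the end of the 20-week follow-up". Section 3.1.1 adds that in their last training module the "professionals learned how to conduct testing of participants and instructed in standardized test protocols".

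**Who coaches.** Section 3.1 says that in HIGH, MEDIUM and LOW "the exercise professionals will prescribe exercise programs tailored to the individual needs". Table 1 says that CONTROL has access to the app "but will not be provided any coaching".

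**Who is masked.** Section 3.1.2 says: "The study design will not allow for further masking of study participants or the exercise professional". Two safeguards follow: "Those from the research group involved in inclusion of the participants or follow-up measurements will not have access to the group allocation list", and "Further, all measurements will be completed and plotted without the research group information of group allocation". On timing, the same section says: "All participants included in the study will conduct the baseline assessments before the randomization procedure".

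**What is held constant.** Section 3.3 fixes each woman's treadmill and strength machine across the two tests. It also fixes the order of tests, the rest intervals, the treadmill speed and incline steps, and a maximum number of lifting attempts. It does not fix the tester or say who tests whom.

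**The concern.** Part of what these tests measure depends on effort or self-report. The strength result is a 1-RM estimated from load and repetition count. Reported RPE is used as a fitness measure, and it also ends the treadmill test, so it sets the point from which heart rate recovery is taken. Encouragement, choice of load steps and counting of repetitions are in the tester's hands.

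A tester who has coached a woman for 20 weeks knows her arm and may want to see progress. A woman in CONTROL has no such tester. If coaches do test their own participants, part of a difference in fitness between a coached arm and CONTROL could come from the testing and not from the coaching. Section 2 says that the pilot is to supply effect sizes for a large-scale study, so a distorted fitness estimate could be carried into that study's planning.

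**Working it through.** The protocol gives no figure for this point, so there is none to reproduce. The check sets the provisions side by side and then counts who could be affected.

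**1. Are testers and coaches the same people?** They are the same group. Section 3.3 gives the tests to the exercise professionals, and sections 3.1 and 3.1.1 give the coaching to them. Whether the same individual does both for one woman is not stated.

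**2. Do the masking provisions reach the testers?** Section 3.1.2 names the exercise professionals as not masked. Its first safeguard is limited to members of the research group. The second speaks of all measurements, but what it withholds is the research group's knowledge of allocation. The likelier reading is that it covers the researchers' handling and entry of data and not the person at the treadmill. It could be misread as a promise of masked assessment.

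**3. When can influence linked to arm act?** Baseline tests come before randomisation, so no tester can know the arm then. Only the week-20 tests are exposed.

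**4. Which measures are exposed?**

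| Measure | Exposure |
|---|---|
| Estimated 1-RM | Effort, load steps and repetition count |
| Reported RPE | Self-report to the tester |
| Treadmill stopping point | Set by a reported RPE of 16 or more |
| Heart rate recovery | Starts wherever the test stopped |
| Sensor heart rate at a fixed stage | Less exposed |

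If the stopping RPE is reached one stage later, the test ends three minutes later at an incline two percentage points higher, and recovery is measured from there.

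**5. How many women could be affected?** Inputs are n = 200 and 1:1:1:1 allocation (sections 3.1 and 3.1.2).
- Expected arm size: 200 / 4 = 50.
- Coached arms: 3 × 50 = 150. This is the ceiling for own-coach testing.
- CONTROL: about 50, of whom none can be tested by her own coach.

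**6. Could another professional do the test?** Inputs are 25 professionals (section 3.1.1) and 12 recruitment locations (section 3.1).
- Per location: 25 / 12 = 2.1 on average.
- Week-20 tests per professional, with no dropout: 200 / 25 = 8 on average, whoever tests whom.

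The number of clubs and the spread of professionals over them are not given, so some clubs may have only one.

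**The case against.** **The protocol is only silent.** A reader might infer that coaches will test their own participants. The document does not say so, and about 150 is a ceiling, not an expected count. Test assignment might be settled in the test protocols and videos that section 3.1.1 mentions. This stands as a limit on the claim. What remains is that unmasked caregivers run the tests and that no rule in the protocol separates the two roles. Who tests, and who is masked, are matters of trial conduct that the protocol itself addresses.

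**It is disclosed and practical.** The protocol says openly that the professionals cannot be masked, and the wide geographical spread makes local testing understandable. That is fair. But being unable to mask a caregiver does not require that caregiver to assess the same woman.

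**The tests are standardised.** Fixed equipment, order, rests, speed, incline steps and attempt limit, with tester training, all narrow the tester's discretion. They do not remove encouragement or repetition counting.

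**The comparison at risk is not the one in the aims.** Aims 1 to 3 are worded as high versus medium versus low. There every woman has a coach, so the influence may partly cancel. The cancellation need not be complete, because planned in-person hours are 20, 10 and 5. The effect-size purpose does not single out fitness either. This lowers the weight but does not remove the exposure in a four-arm trial with a control group.

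**The 1-RM equation is no evidence of bias.** At the same load, one extra repetition multiplies the estimate by (102.78 − 2.78R) / (102.78 − 2.78(R + 1)). This is 100 / 97.22 = 1.029 from one to two repetitions and 80.54 / 77.76 = 1.036 from eight to nine. A reader might infer a bias of 2.9% to 3.6%. That would be wrong: the figures describe the slope of the equation, and nothing in the document suggests that a coach adds a repetition.

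**Conclusion.** The point holds as a minor weakness of design that is cheap to improve. The week-20 fitness tests are in the hands of unmasked professionals who also coach. The protocol does not keep a coach from testing her own participant, and any resulting influence could differ between the coached arms and CONTROL.

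Its size cannot be computed from the document. Fitness is a secondary objective, and the main questions, adherence and total activity, do not rest on these tests. The conclusion assumes that the masking sentences in section 3.1.2 apply to the research group only, which is the likelier but not the only reading. It also assumes that no unseen test procedure already separates tester from coach.

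**What to change.** **(a) Section 3.3, physical fitness.** State that at week 20, in all four arms alike, where the club has more than one trained trial professional, the familiarisation session and the tests are run by one who does not coach that participant and is not told her arm. Familiarisation belongs in the rule because its load becomes the warm-up load for the strength test, so a coach who ran it would still set the starting point.

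**(b) Records and reporting.** Record who tested each woman and whether that person is her coach, and report the counts by arm. Keep all randomised women in the main comparison. Own-coach tests can occur only in coached arms, so dropping them would remove women from those arms alone.

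**(c) Section 3.1.2.** State that fitness testers are unmasked wherever (a) cannot be met.

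I would not also bar the baseline tester from becoming the coach. With about two professionals per location, that would often leave one possible coach.

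**Cost.** Scheduling of the test and familiarisation visits, one or two recorded items, and some wording. No extra staff or tests are needed, since all the professionals are trained in the test protocols. The gain has limits. Masking within a small club will be imperfect, and single-professional clubs gain nothing from (a). Participants know their arm, so their own effort and reported RPE stay unmasked whoever tests.
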